#### **16.5 Analysis of Secondary Endpoints**

The secondary endpoint of overall survival will be analyzed using Kaplan-Meier curves and a log-rank test for the difference between the two therapy groups. Five year OAS, DFS and LRC will be calculated using a log-rank test will be used to test for differences between the two treatment groups.

Toxicity is another secondary endpoint. We will compute for each arm the toxicity rate and provide the corresponding 90% confidence intervals based on the exact binomial distribution.

Reporting and Exclusions

Not Applicable.

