## **1.0 INTRODUCTION**

### **Study Design**

Non-randomized Phase II de-escalation clinical trial to establish recurrence rates, site of recurrence, survival and quality of life outcomes for early T-stage HPV positive oropharyngeal SCCA treated with upfront surgery and reduced dose radiotherapy. Eligible, consented and registered patients will undergo transoral robotic surgery and selective neck dissection. After pathologic evaluation, patients with early stage disease as defined below will be placed into surveillance protocol as outlined or assigned to adjuvant therapy, depending on risk factors. Patients with intermediate risk factors will receive postoperative radiotherapy alone (5000 cGy). Patients with poor prognostic features will receive concurrent chemoradiotherapy (5600 cGy) with weekly cisplatin. Patients taken off study (based on Section 9.2 “Criteria from Removal of Study”) will be followed for survival until the study ends. Any adverse events occurring thereafter in these patients will not be considered related to the study and will not be tracked or reported.

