## **4.0 REGISTRATION PROCEDURES**

After the patient signs the informed consent the patient will be registered for screening and once the investigator has verified that the patient meets all inclusion/exclusion criteria, the patient will be registered for and started on the protocol. Patients who lack p16 and HPV PCR may proceed to surgery however they will not be assigned to an experimental group and registered on the protocol until p16 IHC and HPV PCR are completed and positive. The verification of patient's eligibility and screening completion will be performed centrally after the receipt of the patient primary post-surgical registration form. It is mandatory not to exceed 21 days between the date of registration for screening and the start of the study treatment (surgery). In any case, all events occurring after the registration for therapy must be recorded in the case report form and will be taken into account in the analysis, whether the patient received the study treatment or not. Patient must receive surgery and be p16 IHC and HPV PCR positive to be included in the intent to treat analysis. Patients found to not meet entry criteria will be offered best therapy.

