### **4.1 General Guidelines**

Clinicians will register eligible participants with the Clinical Trial Office. Registration must occur prior to the initiation of screening, again prior to therapy, and finally at completion of therapy for assignment. Any participant not registered to the protocol before treatment begins will be considered ineligible and registration will be denied.

A member of the study team will confirm eligibility criteria and complete the protocol-specific eligibility checklist for final registration.

Following registration for therapy, participants will have surgery on study and following surgery re-registration and assignment to treatment group. Issues that would cause treatment delays should be discussed with the Principal Investigator. If a participant does not receive protocol therapy and assignment treatment following registration, the participant's protocol status must be changed to registered not treated. Notify the registrar of participant status changes as soon as possible. Patients who are eligible and do not receive study surgery will be analyzed in a separate cohort.

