## 5.0 TREATMENT PLAN

### Determination of Stage

Clinical stage will be based on clinical exam, and office based endoscopic evaluation with flexible endoscopy of the upper aerodigestive tract as well as radiographic evaluation with CT and/or MRI in conjunction with CT/PET. Formal operative endoscopy with biopsy under general anesthesia will be performed as indicated when diagnostic or staging dilemma occurs. A preoperative tissue biopsy will be taken and used for histopathological analysis and assignment of p16 status and, if possible, HPV status. All biopsies performed outside the institution will be internally reviewed by pathology department according to protocol guidelines and repeat biopsies will be obtained if there is inadequate tissue for analysis. All patients will be presented and reviewed at multidisciplinary tumor board. Final staging will be performed according to standard 8th Edition AJCC TNM criteria.

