### **6.2 Criteria for Removal from Study**

Participants will be removed from study when any of the criteria listed below applies. The reason for study removal and the date the participant was removed must be documented in the study-specific case report form (CRF). Alternative care options will be discussed with the participant.

In the event of unusual or life-threatening complications, participating investigators must immediately notify the Principal Investigator, [name] at [contact]

- Patient is removed early from protocol therapy at PI's discretion
- Patient is found ineligible
- Patient completion of protocol requirements
- Unacceptable toxicity
- Pregnancy
- Adverse Event
- Progressive disease/ relapse
- Lost to follow-up (documented 3 attempts via telephone or signature confirmation letter)

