## 11.0 MEASUREMENT OF EFFECT

### 11.1.1 Definitions

Evaluable for toxicity. All participants who go on to surgery will be evaluable for toxicity from the time of their first treatment. Patients who are screened will be evaluated and the reason for screen failure will be recorded

Evaluable for Primary Outcome: Only patients who are entered and have surgery will be eligible for assessment of the primary outcomes (LRC, PFS). All patients who have had surgery will be analyzed on an ITT for LRC, PFS, and survival.

Progression-Free Survival: Progression-Free Survival (PFS) is defined as the duration of time from start of treatment to time of objective disease progression or death.

Local Regional Control (LRC) will be defined as local and regional control of disease, censored for death.

Overall Survival (OAS) will be defined as alive at the time of analysis, this will be analyzed as for the entire trial, for all randomized patients and only for those patients randomized who received one dose of radiotherapy.

Post Recurrence LRC: Surveillance Patients who recur will be assessed for LRC post treatment for their initial recurrence

Post Recurrence PFS Surveillance Patients who recur will be assessed for PFS post treatment for their initial recurrence

Ultimate Disease Control will be defined as those patients who are alive and disease free at the time of analysis

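### A patient operated on and later found p16- or HPV-negative is toxicity-evaluable but in no reported toxicity rate, and the Study Design paragraph conflicts with the 30-day adverse-event rules

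*Combined protocol and SAP*

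**What the plan says.** **Who is evaluable.** Section 11.1.1: "All participants who go on to surgery will be evaluable for toxicity from the time of their first treatment". Section 4.0 identifies surgery as the study treatment, so counting starts there.

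**What will be estimated.** Section 16.5: "We will compute for each arm the toxicity rate", with an exact binomial 90% interval. Section 14.2 repeats the sentence. Neither place gives a grade, a time window or a treatment phase.

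**How a patient gets an arm.** Section 4.0 says of patients without marker results: "they will not be assigned to an experimental group and registered on the protocol until p16 IHC and HPV PCR are completed and positive". Yet that section also allows the operation to come first: "Patients who lack p16 and HPV PCR may proceed to surgery". Section 4.2 lets patients register for surgery without the marker results and makes the arm depend on surgical pathology. Under Determination of Stage in 5.0, the preoperative biopsy serves for "assignment of p16 status and, if possible, HPV status". Section 4.1 provides for the opposite case: "Patients who are eligible and do not receive study surgery will be analyzed in a separate cohort".

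**What happens after removal.** Section 3.2.6 excludes p16- or HPV-negative disease. Section 6.2 lists "Patient is found ineligible" as a reason for removal. The Study Design paragraph in 1.0 says of patients taken off study: "Any adverse events occurring thereafter in these patients will not be considered related to the study and will not be tracked or reported".

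**What the safety sections require.** Section 4.0 requires every event after registration for therapy to be recorded on the case report form and considered in the analysis. Section 13.4.1 requires SAE reporting to 30 days after the last treatment. Section 13.7 requires events within 30 days of the last study intervention to be followed to resolution, stability, irreversibility or loss to follow-up.

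**The concern.** Surgery is the one treatment that every participant receives, and toxicity is a named secondary endpoint. The plan declares one population (everyone operated on) and then estimates only in subsets defined after surgery. The subsets do not add up to the population, because marker-negative operated patients belong to none of them.

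The second problem concerns conduct. A site that follows the Study Design paragraph could stop recording on the day the negative marker result leads to removal, while postoperative events are still arising, and would deem those events unrelated. A site that follows 13.7 would continue to day 30. The two sites would hold different data on the same kind of patient.

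At stake are the completeness of the count of surgical events and consistent practice between sites. Sample size, error rates and the efficacy conclusions are not affected.

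**Working it through.** The plan states no toxicity rate, threshold or toxicity sample size, so there is no figure to reproduce. The check has two parts.

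**1. Tracing one patient through the text.** Take a patient operated on with marker results pending, who then tests HPV-negative.

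| Question | Answer | Source |
|---|---|---|
| Registered for therapy before surgery? | Yes; marker results not needed | 4.1, 4.2 |
| Evaluable for toxicity? | Yes | 11.1.1 |
| Assigned to a group? | No | 4.0 |
| In the per-arm toxicity rate? | No | 16.5, 14.2 |
| In the separate cohort? | No; it is for patients not operated on | 4.1 |
| Events recorded and considered in analysis? | Yes | 4.0 |
| SAEs and other events covered to day 30? | Yes | 13.4.1, 13.7 |
| Events tracked after removal as ineligible? | No | 1.0 with 6.2 |
| Saved by the follow-up extension? | No; it covers only removal for unacceptable adverse events | 6.1 |

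The last two rows contradict the two above them. Section 4.0 limits only the intent-to-treat analysis to marker-positive patients, so it does not cancel toxicity evaluability.

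**2. Size.** Inputs from the documents: 200 subjects in all (14.2 gives 100 as half) and 100 in Group I (16.2). The number m of unassigned operated patients is not given. I assume 4, 10 or 20, either within the 200 or on top of it.

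*Chance that at least one of two severe surgical events falls in a patient with no arm*, with events falling at random among N operated patients: 1 − [(N−m)(N−m−1)] / [N(N−1)].

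| m | N = 200 | N = 200 + m |
|---|---|---|
| 4 | 4.0% | 3.9% |
| 10 | 9.8% | 9.3% |
| 20 | 19.0% | 17.4% |

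For example, m = 10 and N = 200: 1 − (190 × 189)/(200 × 199) = 1 − 35,910/39,800 = 9.8%.

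*Bias.* At equal risk it is nil. If the risk were 10% in the arms and 20% in the unassigned (both assumed), the all-operated rate within 200 would be 10% + 10% × m/200, which is 10.2%, 10.5% or 11.0%.

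*Unrecorded time if the Study Design paragraph prevailed.* With removal on day d after surgery (assumed), the share of the 30-day window lost is (30 − d)/30: 77% for d = 7, 53% for d = 14 and 30% for d = 21. This is a share of days, not of events, and it is zero if 4.0, 13.4.1 and 13.7 prevail.

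*Precision of an all-operated rate* (exact 90% intervals):

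| Observed rate | 100 patients | 200 patients |
|---|---|---|
| 0% | upper limit 2.95% | upper limit 1.49% |
| 5% | 2.0–10.2% | 2.7–8.3% |
| 10% | 5.5–16.4% | 6.7–14.2% |

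The narrower intervals come from pooling. They are a benefit of the fix, not evidence of an error.

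**The case against.** The strongest reply is that the plan already handles the main case. Section 4.0 requires events after registration for therapy to be recorded and considered, and that registration precedes surgery. Section 13.4.1 requires SAE reporting to day 30 with no exception for ineligible patients. Section 13.7 also asks investigators to report deaths and events after participation ends that may reasonably be related. Section 14.2 lets the monitoring board see a summary of surgical complications. This reply largely stands. A reader might infer that severe surgical events in marker-negative patients will be lost; the documents do not support that. What remains is one general sentence in 1.0 that contradicts these specific rules, and the lack of any defined rate that includes these patients.

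A second reply is that 16.5 says only each arm, and nearby text speaks of two therapy groups, so assignment after surgery is an inference. That is fair. But 4.0 to 4.2 describe no arm assigned before surgery, and the two-group reading also depends on what follows surgery.

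A reader might also infer that the Group II and III rates cannot be interpreted because they mix surgical and adjuvant toxicity. That holds only if events are counted from surgery, and even then events are dated (13.7) and attributed (13.1.4), so the phases can be separated later. Group I's rate is already surgery-only.

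**Conclusion.** The concern holds as a gap in reporting and a conflict between rules. The declared toxicity population contains patients who appear in no specified rate, and one sentence in 1.0, read with 6.2, would stop tracking that 4.0, 13.4.1 and 13.7 require.

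It is small. The number of affected patients is unknown. Screening for features consistent with p16 positivity (3.0) and the preoperative biopsy (5.0) should keep it low. Expected bias in common events is about nil, and no stated decision uses the toxicity rate. The 4% to 19% chances above rest on assumed values of m and on exactly two severe events. The lost-window shares apply only if the Study Design paragraph overrides the safety sections. The change is still worth making, because a written rule that deems early postoperative events unrelated should not stand beside rules that say otherwise.

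**What to change.** 1. Add to the Study Design paragraph in 1.0 and to 6.2:

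> *Patients who had study surgery and are later removed as ineligible (including p16- or HPV-negative) remain under adverse-event recording and reporting until 30 days after surgery, as in 13.4.1 and 13.7; such events are attributed as in 13.1.4.*

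2. Keep the per-arm rate. Add to 16.5 and to its repeat in 14.2:

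> *We will also report the proportion of all operated patients, whatever their later marker result or group, with at least one adverse event of CTCAE grade 3 or higher with onset from surgery to the earlier of 30 days after surgery or the start of adjuvant treatment, with an exact 90% confidence interval.*

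Grade 3 is a suggestion, since 16.5 names no grade. Events after day 30 and before adjuvant treatment stay in the per-arm rate. An adjuvant-phase rate by group is an optional descriptive table; it would not measure late toxicity.

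Cost: one extra table from grades (13.2) and dates (13.7) already collected, and up to 30 days of recording in a few patients, which 13.4.1 and 13.7 already require. No extra patients or procedures are needed.

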### **17.0 PUBLICATION PLAN**

The results should be made public within 24 months of the end of data collection. If a report is planned to be published in a peer-reviewed journal, then that initial release may be an abstract that meets the requirements of the International Committee of Medical Journal Editors. A full report of the outcomes should be made public no later than three (3) years after the end of data collection.

## 19.0 APPENDICES

### Appendix 1: Performance Status Criteria

ECOG Performance Status Scale		Karnofsky Performance Scale	
Grade	Description	Percent	Description
0	Normal activity. Fully active, able to carry on all pre-disease performance without restriction.	100	Normal, no complaints, no evidence of disease.
		90	Able to carry on normal activity; minor signs or symptoms of disease.
1	Symptoms, but ambulatory. Restricted in physically strenuous activity, but ambulatory and able to carry out work of a light or sedentary nature (e.g., light housework, office work).	80	Normal activity with effort; some signs or symptoms of disease.
		70	Cares for self, unable to carry on normal activity or to do active work.
2	In bed < 50% of the time. Ambulatory and capable of all self-care, but unable to carry out any work activities. Up and about more than 50% of waking hours.	60	Requires occasional assistance, but is able to care for most of his/her needs.
		50	Requires considerable assistance and frequent medical care.
3	In bed >50% of the time. Capable of only limited self-care, confined to bed or chair more than 50% of waking hours.	40	Disabled, requires special care and assistance.
		30	Severely disabled, hospitalization indicated. Death not imminent.
4	100% bedridden. Completely disabled. Cannot carry on any self-care. Totally confined to bed or chair.	20	Very sick, hospitalization indicated. Death not imminent.
		10	Moribund, fatal processes progressing rapidly.
5	Dead.	0	Dead.

CONFIDENTIAL

This document is confidential. Do not disclose or use except as authorized.

## **Appendix 2: Video Swallowing**

The video swallow study report will include the following information:

### **Impressions:**

1. Oropharyngeal findings
  - a. Penetration-Aspiration-Scale
  - b. Severity rating of OP function
    - i. Within Normal Limits
    - ii. Mild
    - iii. Mild-Moderate
    - iv. Moderate
    - v. Moderate-Severe
    - vi. Severe
2. Cervical Esophageal findings
  - a. No stenosis
  - b. Partial stenosis
  - c. Complete stenosis

### **Recommendations:**

1. Diet
  - a. Regular diet
  - b. Soft diet
  - c. Puree diet
  - d. Liquid diet
  - e. G-tube w/trials
  - f. G-tube, NPO
2. Liquids
  - a. Regular
  - b. Thickened
3. Therapeutic precautions/interventions
  - a. Implement postures/strategies to decrease penetration/aspiration or residue

Consider esophageal dilation Yes or No

### **Appendix 3: QOL Questionnaires**

Name \_\_\_\_\_ Date \_\_\_\_\_ Hospital Number \_\_\_\_\_

#### **The M. D. Anderson Dysphagia Inventory**

This questionnaire asks for your views about your swallowing ability. This information will help us understand how you feel about swallowing.

The following statements have been made by people who have problems with their swallowing. Some of the statements may apply to you.

Please read each statement and circle the response which best reflects your experience in the past week.

My swallowing ability limits my day-to-day activities.

**Strongly Agree      Agree      No Opinion      Disagree      Strongly Disagree**

E2. I am embarrassed by my eating habits.

**Strongly Agree      Agree      No Opinion      Disagree      Strongly Disagree**

F1. People have difficulty cooking for me.

**Strongly Agree      Agree      No Opinion      Disagree      Strongly Disagree**

P2. Swallowing is more difficult at the end of the day.

**Strongly Agree      Agree      No Opinion      Disagree      Strongly Disagree**

E7. I do not feel self-conscious when I eat.

**Strongly Agree      Agree      No Opinion      Disagree      Strongly Disagree**

E4. I am upset by my swallowing problem.

**Strongly Agree      Agree      No Opinion      Disagree      Strongly Disagree**

P6. Swallowing takes great effort.

**Strongly Agree      Agree      No Opinion      Disagree      Strongly Disagree**

E5. I do not go out because of my swallowing problem.

**Strongly Agree      Agree      No Opinion      Disagree      Strongly Disagree**

**CONFIDENTIAL**

This document is confidential. Do not disclose or use except as authorized.

F5. My swallowing difficulty has caused me to lose income.

Strongly Agree      Agree      No Opinion      Disagree      Strongly Disagree

P7. It takes me longer to eat because of my swallowing problem.

Strongly Agree      Agree      No Opinion      Disagree      Strongly Disagree

P3. People ask me, "Why can't you eat that?"

Strongly Agree      Agree      No Opinion      Disagree      Strongly Disagree

E3. Other people are irritated by my eating problem.

Strongly Agree      Agree      No Opinion      Disagree      Strongly Disagree

P8. I cough when I try to drink liquids.

Strongly Agree      Agree      No Opinion      Disagree      Strongly Disagree

F3. My swallowing problems limit my social and personal life.

Strongly Agree      Agree      No Opinion      Disagree      Strongly Disagree

F2. I feel free to go out to eat with my friends, neighbors, and relatives.

Strongly Agree      Agree      No Opinion      Disagree      Strongly Disagree

P5. I limit my food intake because of my swallowing difficulty.

Strongly Agree      Agree      No Opinion      Disagree      Strongly Disagree

P1. I cannot maintain my weight because of my swallowing problem.

Strongly Agree      Agree      No Opinion      Disagree      Strongly Disagree

E6. I have low self-esteem because of my swallowing problem.

Strongly Agree      Agree      No Opinion      Disagree      Strongly Disagree

P4. I feel that I am swallowing a huge amount of food.

Strongly Agree      Agree      No Opinion      Disagree      Strongly Disagree

F4. I feel excluded because of my eating habits.

Strongly Agree      Agree      No Opinion      Disagree      Strongly Disagree

Thank you for completing this questionnaire!

CONFIDENTIAL

This document is confidential. Do not disclose or use except as authorized.

Name \_\_\_\_\_ Date \_\_\_\_\_ Hospital Number \_\_\_\_\_

### Xerostomia Questionnaire (XQ)

This questionnaire asks your view about your dry mouth issue. This information will help us understand how you feel about dry mouth. Please rate your response which best reflects your experience in the past week. The higher the score, the worse your dry mouth.

1. Rate your difficulty in talking due to dryness

0    1    2    3    4    5    6    7    8    9    10

2. Rate your difficulty in chewing due to dryness

0    1    2    3    4    5    6    7    8    9    10

3. Rate your difficulty in swallowing solid food due to dryness

0    1    2    3    4    5    6    7    8    9    10

4. Rate the frequency of your sleeping problems due to dryness

0    1    2    3    4    5    6    7    8    9    10

5. Rate your mouth or throat dryness when eating food

0    1    2    3    4    5    6    7    8    9    10

6. Rate your mouth or throat dryness while not eating

0    1    2    3    4    5    6    7    8    9    10

7. Rate the frequency of sipping liquids to aid swallowing food

0    1    2    3    4    5    6    7    8    9    10

8. Rate the frequency of sipping liquids for oral comfort when not eating

0    1    2    3    4    5    6    7    8    9    10

Thank you for completing this survey.

CONFIDENTIAL

This document is confidential. Do not disclose or use except as authorized.

